## Summary

Diabetic ketoacidosis (DKA) is a medical emergency that is associated with significant morbidity and mortality for both patients with type I and type II diabetes. DKA is diagnosed with a blood glucose level > 250 mg/dL, pH <= 7.3, sodium bicarbonate level of <= 18 mEq/L, an anion gap > 10, and the presence of urine and/or serum ketones. Insulin is one of the main treatment modalities for DKA. By correcting hyperglycemia and inhibiting the release of free fatty acids, insulin administration leads to decreased ketone formation and resolution of acidosis. Short-acting (Regular) intravenous insulin is often preferred to subcutaneous administration for initial management due to its short half-life and ease of titration, but patients will eventually need to transition to subcutaneous insulin prior to discharge. This transition will likely include the administration of long-acting, basal insulins such as insulin glargine (Semglee®, Lantus® or Basaglar®) or insulin degludec (Tresiba®), which have a slow onset of action and have an extended duration of action. The timing of initiation or resumption of home long-acting subcutaneous insulin is controversial in the treatment of DKA. Traditionally, patients are transitioned from IV to subcutaneous insulin once the patient reaches a blood glucose level of < 200 - 250 mg/dl and experiences two of the following: anion gap closure ( $\leq 12$  mEq/L), resolution of acidosis (pH > 7.3), and/or a sodium bicarbonate level of  $\geq 15$  mEq/L. The 2019 American Diabetes Association Standards of Medical Care in Diabetes recommend initiation of basal insulin 2 – 4 hours prior to discontinuation of intravenous insulin. However, the 2014 Joint British Diabetes Societies Inpatient Care Group on The Management of Diabetic Ketoacidosis in Adults, recommend continuing patient's subcutaneous basal insulin during the initial management of DKA.

Small prospective, randomized, controlled, pilot trials have shown early initiation of basal insulin within 2-12 hours of IV insulin infusion initiation can prevent rebound hyperglycemia when the insulin infusion is eventually discontinued. These trials have also shown trends toward decreased time to anion gap closure, resolution of acidosis, and hospital length of stay with no increase in hypoglycemic events. Retrospective studies have also shown decreases in time on insulin infusion and trends toward shorter ICU length of stay, resulting in lower costs to the institution. The optimal dose and initial timing of early basal insulin is unknown. Trials have used initial basal insulin dosing ranging from 0.25 to 0.4 units per kilogram that was initiated anywhere from 2 to 12 hours after the initiation of IV insulin infusion, but no prospective trials have examined resuming the patient's home basal insulin early in the course of DKA treatment.

It is currently unknown if resuming a portion or all of the patient's home basal regimen during the initial treatment phase of DKA will provide an impact on patient care. The objective of this study is to evaluate the impact of early glargine administration at a dose of 0.2 units/kg if the patient was not previously on basal insulin or resuming the patient's home basal insulin regimen within two hours after the start of the intravenous insulin infusion in addition to usual care. We will conduct a prospective, randomized study comparing initiation early glargine administration to current standards of care. Outcomes include patient length of hospitalization, ICU length of stay, time to resolution of acidosis and anion gap closure, incidence of hypoglycemia, and incidence of rebound hyperglycemia.

One of the major benefits of this study is its utter simplicity. We will only have one intervention, and only in the intervention group (starting long-acting insulin early along with IV insulin therapy). The control group (standard of care group (SOC)) will be treated as they have been historically using the Regions Hospital DKA treatment protocol. We are not asking for more labs or nursing/provider interventions than usual. We are also not asking more of our pharmacists besides making at most 1-2 more doses of long-acting insulin for patients in the intervention group. This small intervention can help reduce ICU and hospital LOS, time on IV insulin infusion, and total amount of IV insulin administered- all of which will lead to a much greater cost reduction than 1-2 extra doses of long-acting insulin. As an added bonus, per preliminary reports (discussed below) giving long-acting insulin along with the IV insulin infusion does not lead to any additional adverse events, including hypoglycemia.

## Study aims

Primary Outcome:

- 1) Does early administration of insulin glargine result in a shorter ICU length of stay when compared to usual care for the treatment of diabetic ketoacidosis?

Hypothesis: Early administration of insulin glargine will result in shorter ICU length of stay when compared to usual care in patients with DKA.

Secondary Outcomes:

- 1) Does early administration of insulin glargine result in a shorter hospital length of stay (defined as time between start of insulin infusion and discharge from hospital) when compared to usual care for the treatment of diabetic ketoacidosis?

Hypothesis: Early administration of insulin glargine will result in shorter hospital length of stay when compared to usual care in patients with DKA.

- 2) Does early administration of insulin glargine result in a faster recovery from DKA (defined as blood glucose < 200 and two of: Anion Gap  $\leq$  12, Serum Bicarbonate  $\geq$  15 mEq/L, or pH > 7.3) when compared to usual care for the treatment of diabetic ketoacidosis?

Hypothesis: Early administration of insulin glargine will result in a faster recovery from DKA (defined as blood glucose <200 and two of: Anion Gap  $\leq$  12, Serum Bicarbonate  $\geq$  15 mEq/L, or pH > 7.3) when compared to usual care for the treatment of diabetic ketoacidosis.

- 3) Does early administration of insulin glargine result in a shorter duration of elevated anion gap (defined as time with anion gap > 12) when compared to usual care for the treatment of diabetic ketoacidosis?

Hypothesis: Early administration of insulin glargine will result in a shorter duration of elevated anion gap (defined as time with anion gap > 12) when compared to usual care for the treatment of diabetic ketoacidosis.

- 4) Does early administration of insulin glargine result in a shorter duration of time on IV insulin infusion when compared to usual care for the treatment of diabetic ketoacidosis?

Hypothesis: Early administration of insulin glargine will result in a shorter duration of time on IV insulin infusion when compared to usual care for the treatment of diabetic ketoacidosis.

- 5) Does early administration of insulin glargine result in a lower prevalence of rebound hyperglycemia, defined as blood glucose > 180 mg/dL in the 24 hours after IV insulin infusion discontinuation, when compared to usual care for the treatment of diabetic ketoacidosis?

Hypothesis: Early administration of insulin glargine will result in a lower incidence of rebound hyperglycemia, defined as blood glucose > 180 mg/dL in the 24 hours after IV insulin infusion discontinuation, when compared to usual care for the treatment of diabetic ketoacidosis?

- 6) What is the prevalence of a hypoglycemic (defined as blood glucose < 70mg/dL) event occurring while on IV insulin therapy or in the 24h hours after IV insulin infusion discontinuation with early insulin glargine administration compared to usual care?

Hypothesis: The occurrence of a hypoglycemic event occurring while on IV insulin therapy or in the 24h hours after IV insulin infusion discontinuation with administration of insulin glargine is comparable to usual care.

- 7) Does early administration of insulin glargine result in a statistically lower mean blood glucose value in the 24 hours and (separately) 48 hours after IV insulin infusion discontinuation?

Hypothesis: Early administration of insulin glargine will result in a lower mean value of blood glucose in the 24 and 48 hours after IV insulin infusion discontinuation.

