## **Background, Rationale, Significance**

In 2014, there were 168,000 hospitalizations for DKA, and the average length of stay was 3.4 days in 2009. The estimated annual direct medical expense and indirect cost is 2.4 billion dollars per year. DKA is a potentially life-threatening condition due to its ability to cause metabolic acidosis, electrolyte imbalances, and dehydration. While DKA treatment protocols differ from institution to institution, the goals of treatment remain the same --- resolution of acidosis, dehydration, and hyperglycemia. Following fluid resuscitation, correction of hyperglycemia with insulin therapy is the mainstay of treatment. Intravenous (IV) insulin infusions with regular insulin are commonly used due to its short half-life of 30 to 60 minutes and resulting titratability. Treatment is then continued with subcutaneous (SC) insulin once the acidosis and anion gaps have cleared and the patient's hemodynamics and electrolytes abnormalities have resolved. At Regions Hospital, the current criteria for transitioning from IV to SC insulin include meeting the following criteria: 1) fasting blood glucose levels are stable between 180-250 mg/dL for at least 4 hours, 2) vital signs, potassium, and sodium levels are stable and within the normal range, 3) the metabolic acidosis has cleared (anion

gap  $<15$ , and either arterial pH  $\geq 7.3$  or venous pH  $\geq 7.27$ ), and 4) the patient is able to eat regular meals. Traditionally, when SC insulin is initiated, the IV insulin infusion is stopped two hours later. However, the timing of SC initiation has becoming more controversial in recent years. The 2019 American Diabetes Association Standards of Care recommend transition of patients from IV to SC insulin requires administration of basal insulin 2–4 h prior to the intravenous insulin being stopped to prevent recurrence of ketoacidosis and rebound hyperglycemia. However, the 2014 Joint British Diabetes Societies Inpatient Care Group recommend continuing a patient's home basal insulin during the initial management of DKA to prevent rebound hyperglycemia and to avoid extending length of stay. Several recent papers have examined early basal insulin administration as adjunct therapies with IV insulin infusions for the treatment of hyperglycemia and DKA.

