### Statistical analysis plan

The primary outcome and secondary outcomes 1-4 and 7 will follow the same analysis plan to study the difference in the distribution of time to an endpoint. First, the distributions for each of these outcomes will be evaluated to determine if the distribution is normal or non-parametric. If the distribution is normal, that outcome will be analyzed using a two-tailed unpaired t-test. If the distribution is non-parametric, that outcome will be analyzed using a Wilcoxon rank sum test. We expect length of stay data to follow a non-parametric distribution. In secondary outcome 2, the outcome measured is the time at which all of the necessary criteria are hit for the first time simultaneously, which accounts for the transient nature of some of these measures.

Secondary outcomes 5-6 will measure the prevalence of each of these outcomes. Prevalence was chosen over incidence in order to account for multiple instances of rebound hyperglycemia or hypoglycemia occurring within the specified timeframe for each and also the amount of time it takes to clinically reverse these conditions. For both of these outcomes, a two-proportion z test will be run to find the difference in the amount of time each treatment arm cumulatively spent with the specified condition. Finally, for the outcomes relying on certain lab values, we will examine time from IV insulin infusion start to outcome labs in both groups. If there is significant variability between the experimental and SOC arms, we will adjust for this statistically. Group randomization should ensure that variability is

equally distributed between groups, however, there is a chance of bias (e.g., if the experimental group fares better and thus are slower to get nursing checks.)

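### Secondary outcomes 2 and 3 are lab-defined times that can go unobserved, and the planned t or Wilcoxon test has no rule for patients without one

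*Combined protocol and SAP*

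**What the plan says.** Study aims defines secondary outcome 2 as "faster recovery from DKA (defined as blood glucose < 200 and two of" anion gap (AG) at most 12, bicarbonate at least 15 and pH above 7.3. The Statistical analysis plan adds that "the outcome measured is the time at which all of the necessary criteria are hit for the first time simultaneously". Secondary outcome 3 is the time with AG above 12.

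Background, Rationale, Significance gives the site's rule for moving from IV to subcutaneous insulin. Its glucose part is "fasting blood glucose levels are stable between 180-250 mg/dL for at least 4 hours". Its acidosis part is AG below 15 with arterial pH of at least 7.3 or venous pH of at least 7.27. Stable normal vital signs, potassium and sodium, and the ability to eat, are also required. Traditionally, "when SC insulin is initiated, the IV insulin infusion is stopped two hours later".

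No labs are added for the study: "We are not asking for more labs or nursing/provider interventions than usual" (Summary). Under Enrollment, data are abstracted through the stay and at discharge.

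For these outcomes the Statistical analysis plan says that, if normal, "that outcome will be analyzed using a two-tailed unpaired t-test"; otherwise, "If the distribution is non-parametric, that outcome will be analyzed using a Wilcoxon rank sum test". It gives no observation window, no censoring rule and no value for a patient who is never seen to recover. Its one related provision is an unspecified adjustment if lab timing differs significantly between arms.

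**The concern.** Both tests need a value for every patient. Recovery time exists only if a glucose below 200 and two qualifying acid-base results are recorded together. A patient who leaves IV insulin before that point depends on whatever routine labs follow, and glucose checks alone cannot complete the set. With no rule in the plan, the easy course at analysis is to drop patients without a time. That is a post-randomization exclusion based on the outcome. If the missed recoveries are the late ones, it removes the slowest patients, and more of them from the slower arm. The estimated benefit shrinks and power is lost. Settling the rule after the data are seen would also leave a choice that could move the result.

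**Working it through.** **1. The two rules side by side.**

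| Item | Recovery (outcome 2) | Leaving IV insulin |
|---|---|---|
| Glucose | < 200, one reading | 180-250, stable at least 4 h |
| Anion gap | <= 12 (one of a two-of-three set) | < 15 |
| pH | > 7.3 (one of the set) | arterial >= 7.3 or venous >= 7.27 |
| Bicarbonate | >= 15 (one of the set) | not listed |
| Other | none | vital signs, potassium, sodium, eating |

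- Glucose 220 fits the transition range and fails recovery, whatever the acid-base results.
- Venous pH 7.28 with AG 14 fits the transition rule and fails two of the three acid-base items, so bicarbonate cannot rescue it.
- AG 13 or 14 fits the transition rule while outcome 3 is still running.
- In the other direction, glucose 190 with AG 14, bicarbonate 16 and pH 7.32 satisfies recovery and the glucose and acidosis parts of transition.

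Neither rule contains the other, but transition before recovery is possible.

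**2. The plan's own figure.** The Sample size section gives 80% power for length of stay with 66 per arm, ratio 1.31, CV 0.6 and alpha 0.05. Log SD = sqrt(ln(1 + 0.6²)) = 0.5545; ln(1.31) = 0.2700; standard error = 0.5545 × sqrt(2/66) = 0.0965. Power = Φ(0.2700/0.0965 − 1.96) = 79.9%, which reproduces it. No power or missing-data figure is given for outcomes 2 and 3.

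**3. How many times might be unobserved.** This must be assumed. Take recovery as log-normal (median m, log SD s) and the last qualifying labs as log-normal with median L and log SD 0.3, independent of recovery. The unobserved share is 1 − Φ(ln(L/m)/sqrt(s² + 0.3²)). For L, 24 h is about the site's mean infusion length (22.4 + 1.86 = 24.3 h, from its 40-patient sample); 30 h and 48 h are alternatives. Three sets of control recovery times:

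- A: m = 17 h, CV 0.6, ratio 1.31 (assumed; CV and ratio borrowed from length of stay).
- B: AG closure in the cited 2015 two-center trial, 11.6 ± 6.4 h, giving m = 10.2 h, s = 0.516; ratio 1.31.
- C: acidosis duration in the cited 2015 single-center trial, 16.91 ± 6.5 h, giving m = 15.8 h, s = 0.371; ratio 16.91/13.77 = 1.23.

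Example (A, L = 24): ln(24/17)/sqrt(0.5545² + 0.3²) = 0.345/0.630 = 0.547, so 29% of controls. For the intervention arm m = 17/1.31 = 13.0 h, giving about 16.5%.

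**4. Effect on the test.** Simulation, 66 per arm, 5,000 trials per row, two-sided 5%:

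| Set, L | Unobserved, control / intervention | Wilcoxon, nothing lost | Wilcoxon, dropped | Wilcoxon, worst rank | Log-rank, censored |
|---|---|---|---|---|---|
| A, 24 h | 29% / 17% | 77% | 48% | 74% | 71% |
| A, 30 h | 18% / 9% | 77% | 58% | 76% | 72% |
| A, 48 h | 5% / 2% | 77% | 71% | 77% | 72% |
| B, 24 h | 8% / 3% | 82% | 74% | 82% | 78% |
| B, 30 h | 4% / 1% | 82% | 78% | 82% | 77% |
| C, 24 h | 19% / 10% | 87% | 72% | 84% | 82% |
| C, 30 h | 9% / 4% | 87% | 80% | 87% | 82% |

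Repeated runs put the 48% entry between 47% and 50%. In set A the true difference in medians is 17 − 13.0 = 4.0 h; after dropping it averages 2.3, 2.8 and 3.6 h for L = 24, 30 and 48.

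**5. Loss of numbers or bias?** With 20% lost at random, 66 × 0.8 = 52.8 per arm remain and normal-theory power is 70.6%. With 20% lost because they are late, complete-case Wilcoxon power is 45-58% and the estimated ratio falls from 1.31 to 1.17-1.24. Most of the damage comes from which patients are lost. Outcome 3 was not simulated.

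**The case against.** A reader might infer that recovery is simply stricter than the transition rule, that many patients will lack a recovery time, and that the planned tests cannot use them. The documents do not support any of the three.

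- **Stricter.** AG at most 12 is optional within a two-of-three set, and transition carries conditions that recovery lacks, including 4 h of stable glucose. The infusion also traditionally runs two hours past the first subcutaneous dose.
- **Many.** No frequency is given. Abstraction runs to discharge, mean glucose is collected to 48 h after the infusion, and no pH is needed if AG and bicarbonate both qualify. Nothing says that chemistry draws thin out after the infusion, and the hospital's lab schedule is not in the document. The larger losses above follow from assuming that labs end near infusion stop, independently of recovery. With a log-scale correlation of 0.5 between the two, set A's 18-29% becomes 12-24%.
- **Cannot.** A Wilcoxon test can give unobserved recoveries the worst rank, at 74-77% power in set A. The t test has no such device. The plan does not say that such patients are dropped; it is silent.

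Censoring has its own weakness: draws and stays tend to end when clinicians judge the patient improved, so censoring at the last draw or at discharge may be informative.

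All of this stands, and it limits the size of the point. It does not supply the missing rule. Mean glucose to 48 h does not make an acid-base result available, and the promised adjustment for lab timing is undefined and does not address a missing event.

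**Conclusion.** The concern holds in a limited form. Patients can leave IV insulin before documented recovery, or with AG still above 12, and the plan does not say how a patient without an observed time enters the comparison of outcomes 2 and 3.

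The size is conditional. Unobserved recoveries are about 4% to 29% of controls with labs ending at a median of 24-30 h. If they are dropped, Wilcoxon power falls from about 77% to between roughly 50% and 71% with set A and lab end at 24-48 h. The fall is smaller with the cited trials' shorter or less variable times (4 to 15 points in sets B and C). Those cited times are acid-base only; adding glucose below 200 could lengthen them.

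The pull toward no difference assumes that the intervention truly speeds recovery and that labs end at similar times in both arms. If early glargine shortens the infusion, as outcome 4 hypothesizes, labs may end sooner in that arm and the direction is less certain. That is a further reason to fix the window in advance. With no true difference and equal lab-end times, the error rate stays near 5%, so the exposure is a missed or understated effect.

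These are secondary outcomes with no power claim, so the change is advisable and does not threaten the primary analysis.

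**What to change.** For outcomes 2 and 3:

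1. Measure time from the start of the IV infusion over a stated observation window, the same for both arms, and keep every randomized patient.
2. Prespecify one main analysis: a Wilcoxon test with unobserved recoveries given the worst rank, or Kaplan-Meier curves with a log-rank test and a defined censoring time. Use the other as a sensitivity analysis, because censoring at the last draw or discharge may be informative. State how discharge without recovery is handled.
3. Record the time of the last chemistry draw, and report by arm how many patients left IV insulin before meeting the definition.
4. Reconcile the recovery definition in Study aims with the transition rule in Background, or acknowledge the gap. Which threshold is right is a clinical matter and is not judged here.
5. Reconcile the data form (Variable list, sources, and data collection) with the endpoint. It lists first glucose below 250, first AG below 12 and first bicarbonate below 15, against below 200, at most 12 and at least 15 in Study aims. Separate first times also cannot show when criteria were met together, so paired result values and times are needed.

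Cost: some SAP wording, one added time field with the form corrections, slightly more analysis, and a result less simple than a difference in mean hours. No extra labs or patients are needed.

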#### Population

##### Inclusion Criteria

- Presented to Regions Hospital ED for chief complaint of DKA, nausea, vomiting, abdominal pain, hyperglycemia, or similar
- Meets all below diagnostic criteria for DKA per the American Diabetes Association:
  - Arterial or venous pH  $\leq$  7.3
  - Serum Bicarbonate  $\leq$  18 mEq/L
  - Ketonuria or ketonemia
  - Anion Gap  $>$  10
  - Blood sugar  $>$  250 mg/dL
- Receiving IV insulin infusion
- It is feasible to provide insulin glargine within 2 hours (+/- 30 minutes) of IV infusion start
- Will be admitted to the ICU for DKA, or already admitted to the ICU for DKA
- Ability to provide informed consent

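### Entry and recovery cut-offs overlap for anion gap and bicarbonate, so some eligible patients can be scored as recovered on glucose alone and can contribute zero time to the anion-gap outcome

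*Combined protocol and SAP*

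**What the plan says.** **Entry.** The Inclusion Criteria require that the patient "Meets all below diagnostic criteria for DKA per the American Diabetes Association": pH at or below 7.3, bicarbonate at or below 18 mEq/L, ketonuria or ketonemia, anion gap above 10, and glucose above 250 mg/dL. The Summary gives the same limits ("sodium bicarbonate level of <= 18 mEq/L, an anion gap > 10, and the presence of urine and/or serum ketones"), and so does Screening.

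**Secondary outcome 2.** Study aims asks about "faster recovery from DKA (defined as blood glucose < 200 and two of" three components: anion gap at or below 12, bicarbonate at or above 15 mEq/L, and pH above 7.3. The Statistical analysis plan times this at the first moment the required criteria hold together.

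**Secondary outcome 3.** Study aims asks about a "shorter duration of elevated anion gap (defined as time with anion gap > 12" mEq/L). Both outcomes are compared by a t-test or a Wilcoxon rank sum test, depending on the distribution.

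**Data form.** The variable list records presenting pH, bicarbonate, anion gap and glucose. Its timing fields are first pH above 7.3 (labelled an outcome), first anion gap below 12, first bicarbonate below 15, and first glucose below 250.

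No section requires a baseline gap above 12 or a baseline bicarbonate below 15. None makes pH mandatory for recovery or says how to handle patients who already meet acid-base components at presentation.

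**The concern.** A recovery endpoint should start from an unrecovered state. Here two of the three acid-base components can be satisfied by values that also qualify a patient for entry. For a patient in both bands, outcome 2 measures how quickly glucose falls on a titrated insulin infusion and says nothing about whether the acidosis has resolved. For a patient who presents with a gap of 11 or 12, outcome 3 may be zero before any treatment, and a zero cannot be shortened.

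Two things are at stake. A real effect on acidosis would be diluted in both outcomes. A faster recovery under outcome 2 might also be read as faster clearance of ketoacidosis when part of it is a glucose effect.

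**Working it through.** **1. Compare the limits** (Inclusion Criteria against Study aims).

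| Measure | Entry | Recovery | Overlap |
|---|---|---|---|
| Anion gap | > 10 | ≤ 12 | above 10 up to 12 |
| Bicarbonate (mEq/L) | ≤ 18 | ≥ 15 | 15 to 18 |
| pH | ≤ 7.3 | > 7.3 | none |
| Glucose (mg/dL) | > 250 | < 200 | none |

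In whole numbers, the doubly overlapping states are gap 11 or 12 with bicarbonate 15, 16, 17 or 18. That makes 2 × 4 = 8 pairs, at any pH up to 7.30. Each meets exactly two of the three acid-base components at entry. The third is always pH, which cannot overlap.

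**2. Follow one patient.** Take gap 11, bicarbonate 16, pH 7.25 and glucose 300. The patient is eligible, and is not recovered because 300 is not below 200. Let glucose alone fall to 199. Glucose is now met, gap 11 ≤ 12 is met and bicarbonate 16 ≥ 15 is met. Outcome 2 is reached with pH still 7.25. The requirement that criteria hold together guards against transient values, not against components already met at baseline. The same patient has no time above a gap of 12 unless the gap later rises.

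**3. Size.** The Sample size section expects 66 per arm. The documents give no baseline distribution of gap or bicarbonate, so the shares below are assumptions.

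- Gap 11–12 in 5–10%: 0.05 × 66 = 3.3 and 0.10 × 66 = 6.6, so about 3–7 per arm.
- The group in both bands lies inside the gap band, so it is also at most about 3–7 per arm. If bicarbonate 15–18 occurred in 20–40% independently of the gap, it would be 0.05 × 0.20 × 66 = 0.7 to 0.10 × 0.40 × 66 = 2.6, or about 1–3 per arm.

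**4. What zeros cost outcome 3.** The plan's only power figure is for length of stay: ratio 1.31, coefficient of variation 0.6, 66 per arm, alpha 0.05. It reproduces. The log-scale SD is √ln(1 + 0.6²) = 0.5545. The ratio detectable with 80% power is exp[(1.960 + 0.842) × 0.5545 × √(2/66)] = 1.31, and power at 1.31 is 79.9% (normal approximation) or 79.3% (noncentral t).

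Borrow that spread and ratio for outcome 3, purely as illustration, and let a fraction p in each arm be zero. Keeping the zeros scales the Wilcoxon signal by about (1 − p)². Dropping them costs only √(1 − p) in precision. The unrestricted statistic is therefore about (1 − p)^1.5 of the restricted one: 0.95^1.5 = 0.93 and 0.90^1.5 = 0.85. Simulated Wilcoxon power:

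| Zeros | All patients | Presenting gap > 12 only |
|---|---|---|
| 5% | about 68% | about 74% |
| 10% | about 58% | about 72% |

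Under these assumptions the restriction gains power although it uses fewer patients.

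**5. Check the form.** Its first gap below 12 differs from the outcome's at or below 12. Its first bicarbonate below 15 runs in the opposite direction to recovery. Its first glucose below 250 differs from below 200. Outcome 2 cannot be computed from these timing fields as written. The form's gap limit does not remove the overlap either, since a gap of 11 still satisfies both entry and closure.

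**The case against.** **The definition is a recognized one.** The Summary presents the same two-of-three structure, with the same acid-base cut-offs, as the traditional criteria for moving to subcutaneous insulin. Keeping it aids comparison with other work, and correcting hyperglycemia is one of the treatment goals in the Background. This stands, and it is why the definition should not be replaced for everyone.

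**The affected group may be small.** Patients must also have pH at or below 7.3, be on an IV insulin infusion and be bound for or already in the ICU, which may make the double overlap uncommon. This also stands as a limit on size. It does not remove the overlap, and the data to count it are already collected.

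**Zeros in outcome 3 are not certain.** The outcome is time above 12, so a patient presenting at 11 or 12 can contribute time later. That is correct, and restricting the analysis loses this time.

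**Stronger readings that the documents do not support.**

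- *Some patients are fully recovered at entry.* None can be, because glucose must fall from above 250 to below 200.
- *Everyone with bicarbonate 15–18 recovers on glucose alone.* On the assumed 20–40% that would be 13–26 of 66 per arm, but these patients hold only one component and must still reach a gap of 12 or less or a pH above 7.3, unless their gap is also in the overlap.
- *The comparison is biased.* Presenting values precede treatment, and randomization balances them in expectation.

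**Conclusion.** The overlap is certain, because it follows from the plan's own limits and no section removes it. Its practical weight is unknown. On the assumption that 5–10% present with a gap of 11–12, about 3–7 of 66 per arm can contribute zero to outcome 3, and no more than that can reach outcome 2 on glucose alone. The consequence is dilution and a risk of misreading secondary outcomes 2 and 3. ICU length of stay and its power calculation are unaffected. The power figures for outcome 3 also rest on a spread and ratio borrowed from length of stay, so they show direction and rough size only.

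A reader might infer that the recovery rule itself must be rewritten. The documents do not support that, and the obvious rewrites do not work well. Counting a component only if it was unmet at presentation leaves a patient in both bands with pH as the sole countable component, so two of three can never be reached. Raising the bicarbonate limit to above 18 changes the endpoint for every patient and departs from the cited criteria, in order to address a subgroup of unknown size.

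**What to change.** 1. **Outcome 3.** Make the main analysis the patients with presenting anion gap above 12, and report all randomized patients as supportive. The subset is defined by a pre-treatment value already on the form, so the randomized comparison is kept.
2. **Outcome 2.** Keep the two-of-three definition. Report by arm how many patients already met two acid-base components at presentation. Pre-specify a sensitivity analysis that excludes those in both bands. Show time to first pH above 7.3 beside it, stating how many have no repeat pH, since the study requests no extra labs.
3. **Data form.** Reconcile the timing fields for anion gap, bicarbonate and glucose with the outcome 2 definition in Study aims, so that the first moment of joint fulfilment can be derived. This concerns outcome measurement only and implies no change to treatment criteria.

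The cost is a few patients fewer in the main outcome 3 analysis, loss of any later time above 12 among those excluded, a correction to the form, and slightly more analysis. Settle all of it before outcome data are examined by arm.
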